observed. If no additional DLTs are observed in the 6 patients at this dose level, it will be considered the Maximum Tolerated Dose (MTD). If a DLT occurs in 2 patients at any dose level, then the preceding dose level will be considered the MTD. The study will be stopped in the event that 2 DLTs occur at any point in the study.

NUMBER OF PATIENTS 12 to a maximum of 14

INCLUSION CRITERIA

- 1. Age \geq 18 years to \leq 75 years;
- 2. Documented history of Type I or II diabetes with current treatment control (glycosylated hemoglobin A_{1c} of $\leq 10.0\%$);
- 3. Diagnosis of painful diabetic peripheral neuropathy in both lower extremities;
- 4. The physical examination component of the Michigan Neuropathy Screening Instrument Score (MNSI) is ≥ 3 at Screening;
- 5. Visual analog scale (VAS) score of ≥ 4 cm at Screening (0 cm = no pain 10 cm worst imaginable pain);
- 6. Stable treatment of diabetes for at least 3 months with no anticipated changes in medication regimen, and no new symptoms associated with diabetes;
- 7. Lower extremity pain for at least 6 months; and
- 8. If female of childbearing potential, negative pregnancy test at screening and using acceptable method of birth control during the study.

EXCLUSION CRITERIA

- 1. Peripheral neuropathy caused by condition other than diabetes;
- 2. Other pain more severe than neuropathic pain;
- 3. Progressive or degenerative neurological disorder;
- 4. Myopathy;
- 5. Inflammatory disorder of the blood vessels (inflammatory angiopathy, such as Buerger's disease);
- 6. Active infection:
- 7. Chronic inflammatory disease (e.g. Crohn's, Rheumatoid Arthritis)
- 8. Positive HIV or HTLV at Screening
- 9. Positive Hepatitis B or C as determined by Hepatitis B core antibody (HBcAB), antibody to Hepatitis B antigen (IgG and IgM; HbsAB), Hepatitis B surface antigen (HBsAg) and Hepatitis C antibodies (Anti-HCV), at Screening or known immunosuppression or on chronic treatment with immunosuppressive drugs, chemotherapy or radiation therapy;
- 10. Stroke or myocardial infarction within last 6 months;
- 11. Ophthalmologic conditions pertinent to proliferative retinopathy or conditions that preclude standard ophthalmologic examination:
 - Cataract surgery within 6 months of trial;
 - Vascular lesions of the anterior segment of the eye (infection or ulceration of the cornea, rubeotic glaucoma, etc);
 - Vascular lesions of the posterior segment of the eye or proliferative retinopathy, macular edema, s/p

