3.2. STUDY DESIGN

This is a phase I/II, open label, dose-escalation, multicenter, 12 month study. Patients with painful DPN will be screened for study eligibility after giving informed consent. Patients will be treated with 4 mg, 8 mg or 16 mg of VM202 by intramuscular injections in the right calf on Day 0 and again on Day 14. Study drug will only be administered unilaterally. If injection in the right leg is medically contraindicated, the left leg may be treated and noted on the appropriate case report form.

VM202 will be delivered in a solution of 0.5 mg VM202 / mL. Individual injections will be 0.5 mL. Patients in Cohort I will receive 2 mg of VM202 on Day 0 and Day 14 for a final dose of 4 mg; Cohort II will receive 4 mg of VM202 on Day 0 and Day 14 for a final dose of 8 mg; and Cohort III will receive 8 mg of VM202 on Day 0 and Day 14 for a final dose of 16 mg VM202. Table 2 lists the final dose and number of injections to be administered by study cohort. Patients will be followed for a period of 12 months.

Table 2. VM202 administration for each cohort

Сонокт	FINAL DOSE VM202	Number of Injections Day 0 Day 14		TOTAL VOLUME INJECTED
I	4 mg	8	8	8 mL
II	8 mg	16	16	16 mL
III	16 mg	32	32	32 mL

This is a dose escalation study. Cohorts of increasing dose will be enrolled sequentially. Dose escalation decisions (permission to treat at higher doses) will be made by the Data Safety Monitoring Board (DSMB) based on review of adverse events and on the occurrence of dose limiting toxicities (DLT) in each cohort. The decision to proceed to the next higher dose cohort will be made according to the following scheme.

After the first patient in a dose cohort completes the Day 30 follow-up evaluation and the other three patients enrolled in the same cohort complete at least the Day 14 follow-up (second dosing), an interim safety evaluation will be performed by the DSMB.

- If no DLT is observed at the current dose cohort, then the dose may be escalated as planned for the next cohort.
- If a DLT is observed in one patient in a dose group, then 2 additional patients will be treated at the same dose level. If no further DLTs are observed in the additional patients at Day 30, then that Dose will be considered the Maximum Tolerated Dose (MTD).
- If a DLT occurs in 2 patients, then the preceding dose level will be considered the MTD.

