If a DLT is observed in a patient in a dose cohort with complete enrollment, but after a dose escalation has occurred, further dose escalation may be delayed pending review of the data. If 2 patients in a dose cohort experience a DLT, then the study will be stopped.

A DLT is defined as any of the following SAEs:

- acute anaphylaxis (including erythema, hives, wheezing, stridor or respiratory distress) attributable to VM202 injection;
- temperature >102°F with negative blood cultures and in absence of viral syndrome within 24 hours of study drug administration; or
- evidence of active tissue necrosis of grade 3 or greater at the injection site within two weeks of study drug administration.

The DSMB will make a formal recommendation to proceed (or not proceed) to the next dose cohort between the first and second dose cohort, and again between the

second and third dose cohort (if applicable). The DSMB will monitor patient safety throughout the 12 month follow-up period.

[figure not shown]

Figure 3. Study flowchart

Screening/Baseline assessments should occur within the 60 days prior to Day 0 (day of injection). Baseline assessments include assessment of study eligibility, a complete medical history, vital signs, complete physical exam, photograph and measurement of ulcers (if any), cancer screening tests, viral screening, MNSI Score, VAS, 12 lead EKG, retinal fundoscopy, clinical chemistry, hematology, urinalysis, and pregnancy test (women of childbearing potential only), and documentation of any ulcers or gangrenous areas.

Patients will be treated with 8, 16 or 32 – 0.5 mL intramuscular injections in the right calf of VM202 on Day 0 and again on Day 14. Each injection will contain 0.25 mg VM202. The first cohort of patients will receive a total dose of 4 mg of study product in 8 mL of solution (eight injections on Day 0, and eight injections on Day 14). The second cohort of patients will receive a total dose of 8 mg of study product in 16 mL of solution (sixteen injections on Day 0, and sixteen injections on Day 14). The third cohort of patients will receive a total dose of 16 mg of study product in 32 mL of solution (thirty-two injections on Day 0, and thirty-two injections on Day 14).

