3.4.3. SCREENING (DAY -60 TO DAY 0)

Patient enrollment is subject to the rules established in Section 3.2 for dose escalation, but screening procedures can proceed provided the Investigator waits for enrollment confirmation from ViroMed or its Designee.

The following procedures / evaluations will be conducted at screening:

- Obtain informed consent prior to any study-related procedures
- Evaluation of eligibility
- Complete Medical History
- Vital Signs
- Complete Physical Exam
- **Concomitant Medications**
- Cancer screening including cancer markers; pap smear and mammogram if not performed within past 12 months (females only); chest X-ray or CT scan of the chest (if the patient has a previous history of tobacco use, a CT scan will be performed instead of the chest X-ray) within 3 months prior to study entry; PSA (males only); for patients ≥ 50 years old, colonoscopy within past 10 years. Note fecal occult blood test (FOBT) is not required since colonoscopy will be performed to screen for colon cancer.
- Retinal Fundoscopy in cases where fundoscopy alone is deemed insufficient to rule out exclusionary conditions (see exclusion criterion # 11), fluorescein angiography may be conducted
- Viral screening HIV, Anti-Human T-Cell Lymphotropic Virus (HTLV), Positive Hepatitis B or C as determined by Hepatitis B core antibody (HBcAB), antibody to Hepatitis B antigen (IgG and IgM; HbsAB), Hepatitis B surface antigen (HBsAg) and Hepatitis C antibodies (Anti-HCV), at Screening
- Serum chemistry and hematology
- Urinalysis
- Urine pregnancy test (for women of childbearing potential only)
- Photograph and measurement of ulcer(s) if present
- EKG
- Michigan Neuropathy Screening Instrument
- Visual Analog Scale (VAS) score

3.4.3.1. **SCREEN FAILURES**

Patients not meeting all study entry criteria will be designated as a screen failures. End of study procedures will not be performed for these patients, but their reason for discontinuation will be recorded on the CRF. Screen failures will be replaced.

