4.2.11. INJECTION SITE REACTION ASSESSMENT

Local injection sites reactions will be assessed on Day 0 post injection, Day 14, Day 21, Day 30 and Day 60 using the grading defined by the National Cancer Institute's Common Terminology for Adverse Events v3.0. The grading categories are as follows and will be recorded on the CRF as described in

Table 3. Injection Reaction Assessment

Table 3.

ADVERSE EVENT	GRADE 1	GRADE 2	GRADE 3	GRADE 4	GRADE 5
Injection site reaction	Pain, itching, erythema	Pain or swelling, with inflammation or phlebitis	Ulceration or necrosis that is severe; operative intervention indicated		
Ulceration		Superficial ulceration < 2 cm size; local wound care; medical intervention indicated	Ulceration ≥2 cm size; operative debridement, primary closure or other invasive intervention indicated (e.g. hyperbaric oxygen)	Life- threatening consequences; major invasive intervention indicated (e.g., complete resection, tissue reconstruction, flap, or grafting	Death
Allergic reaction / hypersensitivity	Transient flushing or rash; drug fever < 38°C (<100.4°F)	Rash; flushing ; urticaria; dyspnea; drug fever ≥38°C (≥100.4°F)	Symptomatic bronchospasm, with or without urticaria; parenteral medications(s) indicated; allergy- related edema/ angioedema; hypotension	Anaphylaxis	Death

5. **EVALUATION OF ADVERSE EVENTS**

5.1. **DEFINITIONS**

An Adverse Event (AE) is the development of an untoward medical occurrence or the deterioration of a pre-existing medical condition following or during exposure to an investigational product, whether or not considered causally related to the product.

An untoward medical condition can be symptoms (e.g., nausea, chest pain), signs (e.g., tachycardia, enlarged liver) or clinically significant abnormal results of an investigation (e.g., laboratory findings, electrocardiogram).

A serious adverse event (SAE) is any untoward medical occurrence which:

- Results in death;
- Is life-threatening;
- Requires inpatient hospitalization or prolongation of hospitalization which is not specifically required by the protocol or is elective;
- Results in permanent impairment of a body function or permanent damage to a body structure; or
- Requires medical or surgical intervention to preclude permanent impairment of a body function or permanent damage to a body structure.

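### The DSMB escalation review may be held with 0 to 3 of the 4 second-dose necrosis windows still open on nominal days (4 of 4 at the extreme of the visit windows), depending on enrolment stagger

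*Combined protocol and SAP*

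**What the plan says.** **Trigger.** Section 3.2 and the Study Design entry of the synopsis give the same rule. The DSMB reviews a cohort of four after patient 1 completes Day 30 and "the other three patients enrolled in the same cohort complete at least the Day 14 follow-up (second dosing".

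**Decision.** Section 3.2: "If no DLT is observed at the current dose cohort, then the dose may be escalated as planned for the next cohort".

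**DLT definition.** One of the three DLT types in Section 3.2 is "evidence of active tissue necrosis of grade 3 or greater at the injection site within two weeks of study drug administration". Doses are given on Day 0 and Day 14, so each patient has two such windows.

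**After one DLT.** Two patients are added at that dose. Section 3.2 judges them at Day 30: "If no further DLTs are observed in the additional patients at Day 30, then that Dose will be considered the Maximum Tolerated Dose (MTD".

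**DLT in a fully enrolled cohort after escalation.** Section 3.2 says that in this case, "but after a dose escalation has occurred, further dose escalation may be delayed pending review of the data".

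**Stopping.** The synopsis: "The study will be stopped in the event that 2 DLTs occur at any point in the study". Section 3.2 words the stop as two patients with a DLT in one dose cohort.

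**Checks already scheduled.** Section 4.2.11: "Local injection sites reactions will be assessed on Day 0 post injection, Day 14, Day 21, Day 30 and Day 60".

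**The concern.** The escalation decision turns on whether a DLT has been observed. For patients 2 to 4 the plan requires no follow-up beyond the second-dosing visit, yet it goes on counting necrosis for two weeks after that visit. The review can therefore find no DLT before the plan's own definition has been fully applied to the cohort. Patients 2 to 4 are the only ones treated this way: patient 1 and the two expansion patients are taken to Day 30.

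Timing can change what follows. A single DLT seen at the review holds the dose while two more patients are treated, and with no further DLT that dose becomes the maximum tolerated dose (MTD). If the same DLT appears a few days after escalation, the next cohort, at twice the dose, may already have been treated. If it arises in Cohort II after Cohort III has opened, no further escalation is left to delay. Section 6 names finding the MTD as the study's primary goal, so this bears on the main output as well as on patient safety.

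**Working it through.** The plan gives no figure to reproduce here. The check is calendar arithmetic.

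**Inputs**
- Second dose: nominal Day 14, permitted Day 13 to 15 (synopsis, Schedule of Examinations).
- Day 30 visit: permitted Day 27 to 33 (same place).
- Necrosis window: 14 days after each dose (Section 3.2).
- Stagger within a cohort: not fixed in the text available. Figure 3, the flowchart, is not shown. The start days below are assumptions.

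**Nominal days.** Let the patients start on days s1 = 0 ≤ s2 ≤ s3 ≤ s4.
- Earliest review: T = max(30, s4 + 14).
- Days observed after dose 2 for patient i: min(14, max(0, T − (s_i + 14))).
- The window is open at T if s_i + 28 > T.

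| Start days | T | Days observed after dose 2 | Windows open | Window-days unobserved, of 56 |
|---|---|---|---|---|
| 0/0/0/0 | 30 | 14, 14, 14, 14 | 0 | 0 |
| 0/14/28/42 | 56 | 14, 14, 14, 0 | 1 | 14 |
| 0/7/14/21 | 35 | 14, 14, 7, 0 | 2 | 21 |
| 0/3/3/3 | 30 | 14, 13, 13, 13 | 3 | 3 |
| 0/7/14/16 | 30 | 14, 9, 2, 0 | 3 | 31 |
| 0/16/16/16 | 30 | 14, 0, 0, 0 | 3 | 42 |

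Over all whole-day staggers from 0 to 60 days, the number open runs from 0 to 3. It is 0 only when s4 ≤ 2. Once s4 ≥ 16, the last patient needs only the dosing-day check after dose 2.

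**Visit windows.** If patient 1 has dose 2 on Day 15 and the Day 30 visit on Day 27, only 27 − 15 = 12 days have passed and 2 remain. If patients 2 to 4 start on day 13 and have dose 2 on day 27, the review may fall on day 27 with all four windows open.

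**First dose.** With dose 2 no earlier than Day 13, every patient has at least 13 of the 14 first-dose days observed.

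**Chance of a late DLT (illustrative).** The documents give no DLT rate. Let q be an assumed per-patient risk of a second-dose DLT first appearing after the dosing day. With k fully open windows the chance of at least one after the review is 1 − (1 − q)^k. For weekly starts (one window fully open, one half open, even hazard assumed) it is 1 − (1 − q/2)(1 − q).

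| q | No window open | One fully open | Weekly starts | Three fully open |
|---|---|---|---|---|
| 0.02 | 0 | 2.0% | 3.0% | 5.9% |
| 0.05 | 0 | 5.0% | 7.4% | 14.3% |
| 0.10 | 0 | 10.0% | 14.5% | 27.1% |

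**Wait under the fix.** On nominal days the review moves to s4 + 30. The added wait is s4 + 30 − T, which equals s4 up to s4 = 16 and 16 after that. With visit windows, the longest gap from dose 2 to the Day 30 visit is 33 − 13 = 20 days, so the wait never exceeds 20.

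**The case against.** The best defence is that this is a deliberate trade-off. Patient 1 is followed to Day 30, the wording for the others is a minimum, escalation is permitted and not required, and Section 3.2 expressly foresees a DLT after escalation. The DSMB may wait, and it monitors safety for 12 months.

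The gap is also narrow. It concerns mainly second-dose necrosis. The fever DLT has a 24-hour window, which matters only if the review falls on or just after a dosing day, and anaphylaxis is described as acute. The second dose equals the first, each injection is 0.25 mg in every cohort, and Appendix 4 sends the second set to different sites where possible. Section 1.5 reports only mild, transient injection-site irritation, in rats at 11 times an 8 mg dose.

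There are brakes before the next cohort is dosed. SAEs are reportable within 48 hours (Section 5.4.1). Under Section 3.4.3, "screening procedures can proceed provided the Investigator waits for enrollment confirmation from ViroMed or its Designee", and Section 3.4.4 requires authorization for each treatment. Windows go on closing during these steps.

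A reader might infer that a DLT found after escalation leads to nothing more than a possible delay. The documents do not support that. The synopsis adds two patients after one DLT in any dose group, without limiting this to the time before escalation, and a late DLT counts toward the two-DLT stop.

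All of this stands, and it lowers both the probability and the consequence. None of it requires the second-dose windows to close before the next cohort is treated.

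**Conclusion.** The point holds as a gap in timing. At the earliest permitted review, 0 to 3 of the 4 second-dose necrosis windows are open on nominal days, and 4 of 4 at the extreme of the visit windows. Where in that range a cohort falls depends on a stagger that the available text leaves open; a rule in Figure 3 could narrow it. With close starts the shortfall is nil or a few days. With weekly starts it is 21 of 56 window-days, and at worst on nominal days 42 of 56.

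A late DLT still counts toward stopping and, on the synopsis wording, may still add two patients. What is lost is the assurance that it is seen before anyone receives the next dose; on that, Section 3.2 says only that further escalation may be delayed.

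It would be tempting to read the 27% as the risk to the next cohort. It is not an estimate: q is assumed, three fully open windows are the nominal worst case, and the calculation supposes an immediate review and immediate dosing of the next cohort. The percentages are upper bounds at the chosen q. Nor do the documents suggest that such necrosis is likely. The case for change rests on the mismatch between review trigger and DLT window and on how little it costs to remove.

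**What to change.** In Section 3.2 and the synopsis, replace the trigger with: the DSMB escalation review takes place after all four patients in the cohort have completed the scheduled Day 30 visit and at least 14 days have passed since each patient's second dose. The 14-day minimum is needed because a Day 30 visit alone can fall only 12 days after dose 2.

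This brings patients 2 to 4 to the standard already set for patient 1 and the expansion patients, and it uses the Day 21 and Day 30 site checks already scheduled.

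Cost: 0 to 16 nominal days, at most 20 with visit windows, at each of the two escalation steps (0 to 6 days if all four start together, 14 to 20 with weekly starts). The wait is longer only if a patient withdraws before Day 30 and a replacement under Section 3.5.2 has to be followed. No patients, visits or assessments are added, and one sentence changes in each place.

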- I will ensure that any staff at my site(s) who are involved in the study conduct are adequately trained regarding this trial's operations, the protocol and their responsibilities. In the case of delegating any of my study responsibilities I will provide the sponsor with a delegation of investigators responsibilities log.
- I understand that the study may be terminated or enrollment may be suspended at any time by ViroMed, Inc. with or without cause, or by me or my institution if it becomes necessary to protect the best interest of the study patients.

Principal Investigator's Name (print)
mi d
Title
Address
Signature / Date

STUDY SYNOPSIS

PROTOCOL TITLE A Phase I/II, Open Label, Dose-Escalation Study to Assess the

Safety and Tolerability of VM202 in Patients with Painful Diabetic

Peripheral Neuropathy

STUDY PHASE I/II

INVESTIGATIONAL AGENT VM202

Dose Three doses will be tested: 4 mg, 8 mg and 16 mg VM202.

POPULATION Patients aged ≥ 18 years to ≤ 75 years diagnosed with painful

diabetic neuropathy in both lower extremities.

STUDY DESIGN A phase I/II, open label, dose-escalation, multicenter, 12-month

study designed to assess the safety and tolerability of unilateral intramuscular injection in the calf of VM202 in patients with painful diabetic peripheral neuropathy (DPN). The study will consist of three (3) cohorts with a total of 4 patients enrolled in

each cohort.

A Data Safety Monitoring Board (DSMB) will monitor patient safety throughout the study. After the first patient in a dose cohort completes the Day 30 follow-up evaluation and the other three patients enrolled in the same cohort complete at least the Day 14 follow-up (second dosing), an interim safety evaluation will be performed by the DSMB. If the DSMB recommends proceeding, the next dose cohort will be treated. This process will be repeated between the second and third dose cohort. All three dose cohorts will be followed for one year from the time of the first dose of study drug administration. If a dose limiting toxicity (DLT) is observed in one patient in any dose group, two additional patients will be added to the dose cohort in which the toxicity was observed. If no additional DLTs are observed in the 6 patients at

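### The synopsis confirms the MTD on all 6 patients at a dose, Section 3.2 on the 2 added patients at Day 30; after a late second DLT in an original patient the two tests disagree and no precedence is stated

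*Combined protocol and SAP*

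**What the plan says.** The design has "three (3) cohorts with a total of 4 patients enrolled in" each. After one DLT at a level, "2 additional patients will be treated at the same dose level", which makes six.

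The rule that then confirms the MTD appears twice:

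- **Synopsis, Study Design:** "If no additional DLTs are observed in the 6 patients at this dose level, it will be considered the Maximum Tolerated Dose (MTD". It counts all six patients and gives no time point.
- **Section 3.2, second bullet:** "If no further DLTs are observed in the additional patients at Day 30, then that Dose will be considered the Maximum Tolerated Dose". It counts the two added patients and is read at Day 30.

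Both places also have a two-DLT rule that is not limited to the added patients. Section 3.2, third bullet: "If a DLT occurs in 2 patients, then the preceding dose level will be considered the MTD". Synopsis: "If a DLT occurs in 2 patients at any dose level, then the preceding dose level will be considered the MTD".

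The stopping rules differ as well. Section 3.2 says: "If 2 patients in a dose cohort experience a DLT, then the study will be stopped". The synopsis stops the study once two DLTs have occurred anywhere in it. Neither stopping rule says which dose is then the MTD.

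**The concern.** Section 6 makes finding the MTD the primary goal, so the rule that names it should give one answer for any set of data. Here two current texts use different patients and different time limits for the same decision. If a second original patient has a DLT after the expansion has begun and both added patients are clean, the confirmation clause in the second bullet of Section 3.2 is met. So is the two-patient condition in the third bullet. One names the current dose and the other the preceding dose. The current dose would then carry the MTD label with an observed DLT rate of at least 2/6 (33%).

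Section 3.2 does address a late DLT in a fully enrolled cohort, but only once escalation has already taken place. It does not cover one that appears during an expansion.

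**Working it through.** **1. The plan's own figure.** 3 × 4 = 12, and one expansion of 2 gives 14. This reproduces "NUMBER OF PATIENTS 12 to a maximum of 14". The point below does not affect the sample size.

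**2. The rules applied to every outcome.** Let a be the DLTs among the original four (1 to 4) and b those among the added two (0 to 2), giving 4 × 3 = 12 combinations.

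| a | b | Combinations | 3.2, second bullet | 3.2, third bullet | Synopsis |
|---|---|---|---|---|---|
| 1 | 0 | 1 | current dose | not met | current dose |
| 1 | 1 or 2 | 2 | not met | preceding dose | preceding dose |
| 2, 3 or 4 | 0 | 3 | current dose | preceding dose | preceding dose |
| 2, 3 or 4 | 1 or 2 | 6 | not met | preceding dose | preceding dose |

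Read literally, Section 3.2 gives two answers in 3 of the 12 combinations. The synopsis gives one answer in all 12. The three combinations count only if a single DLT triggered the expansion and the others came later. Two DLTs already present at the review never enter the one-DLT bullet.

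**3. Can a second original DLT come after the review?** At the DSMB review the first patient has reached Day 30, but the other three need only have completed Day 14, the second dosing. The tissue-necrosis criterion runs for two weeks after administration. With dosing on Day 14 ± 1, that window closes on Day 13 + 14 = 27 to Day 15 + 14 = 29. So yes.

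**4. What is known when the added patients are read?** Their Day 30 visit (± 3 days) falls at the earliest on their Day 27. If they are dosed no earlier than the review, the original patients are then at Day 13 + 27 = 40 or later, past Day 29. Data on all six would be in hand.

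**5. Scale.** The documents give no DLT risk, so these inputs are assumptions: p, the full DLT risk per patient, and g, the share of that risk falling before the review for the three less-followed original patients. The first patient is taken as fully observed.

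- Expansion (exactly one DLT at review): E = p(1 − pg)³ + 3pg(1 − p)(1 − pg)²
- Same, with no later DLT in the originals: N = p(1 − p)³(1 + 3g)
- Conflict pattern: C = (E − N)(1 − p)²

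With g = 0.5:

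| p | E | N | C, per cohort | C/E, of expansions |
|---|---|---|---|---|
| 0.10 | 0.2076 | 0.1823 | 0.0205 | 9.9% |
| 0.20 | 0.3402 | 0.2560 | 0.0539 | 15.8% |
| 0.30 | 0.4118 | 0.2573 | 0.0757 | 18.4% |

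Moving g from 0.75 to 0.25 gives, per cohort, 1.3–2.4%, 3.2–6.4% and 4.4–9.4%. Of expansions it gives 5.0–15.1%, 8.4–23.0% and 10.3–25.3%.

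**The case against.** The strongest reply is that the three bullets are alternatives by count: none, one patient, two patients. Once a second patient has a DLT, the one-patient bullet no longer describes the cohort and the third bullet governs. The stopping rules point the same way, since a second DLT at the same level meets both. By step 4 it would also be known before the added patients' Day 30 reading.

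Much of this stands. It makes the preceding-dose reading the stronger one. A reader might infer that the DSMB could defend either dose equally well from the text. The documents do not support that, because only one clause favours the current dose. What remains is that the exclusive reading is not written down, the stopping rules name no MTD and differ between the two places, and exclusivity would not remove the mismatch between six patients and two. The Section 3.2 flowchart was not legible in the copy reviewed and may show an order of decision, so the point rests on the text.

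A reader might also put the frequency higher. Placing all of the other three patients' DLT risk after the review gives [1 − (1 − p)³](1 − p)², or 13%, 22% and 28% of expansions at p = 5%, 10% and 15%. The documents do not support that either. Those patients have already reached the second dosing, and the fever criterion closes within 24 hours of each dose.

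Finally, the stated objective and primary endpoint are safety and tolerability, summarised over every treated patient. The DLT counts would therefore be visible whatever the label, and the harm is confined to which dose is called the MTD.

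**Conclusion.** The inconsistency is real and should be corrected. The synopsis and Section 3.2 define MTD confirmation on different patients and with different time limits. In one foreseeable pattern a literal reading of the second bullet names a dose that the rest of the text rules out, and nothing says which prevails.

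The pattern is uncommon: about 2%, 5% and 8% per cohort at assumed DLT risks of 10%, 20% and 30% with half the risk before the review, or 10%, 16% and 18% of expansions. These figures show scale only. The contradiction itself depends on none of them.

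A reader might infer a choice between two dose levels in every cohort. It arises only in Cohort II (8 mg against 4 mg total) and Cohort III (16 mg against 8 mg total). Cohort I has no preceding dose, so there the two-DLT rule has no level to name.

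**What to change.** Reconcile the synopsis and Section 3.2, including the stopping rule in each:

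- Put one identical statement in both places of which patients at the dose level count toward MTD confirmation, and up to what time.
- Word the one-DLT and two-DLT rules so that they cannot both be met by the same data, and so that they agree with a single stopping rule.
- State what is reported as the MTD if the two-DLT rule is met in Cohort I.
- Report the MTD with the DLT count over all patients treated at that dose, not over the added patients alone.

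Which rule applies is for the sponsor and the DSMB to settle, before the data arise. The cost is a wording amendment, with no extra patients, visits or procedures.

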6. STATISTICAL METHODS

The primary goal of this study is to determine the maximum tolerated dose that ensures patient safety. Sample size estimations were not based on formal statistical hypotheses testing due to the exploratory nature of this Phase I/II study. Hypothesis testing will not be performed on any endpoint.

6.1. **PATIENT CATEGORIZATION**

Screen Failure - Any patient who was consented and entered into the screening process appropriately, but subsequently did not meet the entry criteria in order to be treated. Patients who fail screening will not be followed for safety or efficacy assessment, and no other study procedures will be performed.

Evaluable Patient - Any patient who received the study drug.

Lost to follow-up - A patient deemed to be lost to follow-up is any patient who received treatment, but who does not complete scheduled study visits. This includes those patients who withdraw consent and refuse further study participation and all attempts to contact the patient are deemed unsuccessful.

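### The plan gives no single, consistent consequence for one DLT observed after escalation: on one reading that dose becomes the MTD, on another escalation may go on and no MTD rule is triggered

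*Combined protocol and SAP*

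**What the plan says.** Section 6 states: "The primary goal of this study is to determine the maximum tolerated dose that ensures patient safety". No formal sample size stands behind the design: "Sample size estimations were not based on formal statistical hypotheses testing due to the exploratory nature of this Phase I/II study". The decision rules therefore carry the primary result.

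Three pieces of text bear on a single DLT.

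- **Synopsis, Study Design.** When a DLT "is observed in one patient in any dose group, two additional patients will be added to the dose cohort" concerned. The consequence follows: "If no additional DLTs are observed in the 6 patients at this dose level, it will be considered the Maximum Tolerated Dose (MTD". There is no time limit, and no sentence about a DLT seen after the next cohort has opened.
- **Section 3.2, bulleted scheme.** This gives essentially the same rule: two more patients at the same dose, and that dose is the MTD if the added patients are free of DLTs at Day 30. The bullets are introduced as the scheme for deciding whether to move up to the next cohort.
- **Section 3.2, the sentence after the bullets.** For a DLT in a cohort that is already fully enrolled, "but after a dose escalation has occurred, further dose escalation may be delayed pending review of the data". It mentions neither expansion nor the MTD.

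**The concern.** The one-DLT rule, followed to its end, never leads to a higher dose. With no further DLT, the affected dose is the MTD. With a second DLT in that cohort, the preceding dose is the MTD. The late-DLT sentence points elsewhere: something that may be delayed may also resume, and the permissive verb makes even the pause optional. If the bullet still governs after escalation, the sentence has nothing left to delay. If the sentence replaces the bullet, the synopsis lacks the exception.

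The text does not say which is meant. At stake are whether patients go on to a higher dose after the event and whether the trial has a defined MTD. None of the three pieces of text says what happens to patients already in the open higher cohort, including those awaiting their Day 14 injections, while the event is reviewed.

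**Working it through.** **1. The plan's own figure.** The synopsis has "three (3) cohorts with a total of 4 patients enrolled in" each: 3 × 4 = 12. One expansion adds two: 12 + 2 = 14. This reproduces the stated "12 to a maximum of 14". It does not settle the question. The 12 is the total with no DLT, and a Cohort I DLT seen before escalation already gives 4 + 2 = 6 if 4 mg is then the MTD.

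**2. Can the event occur?** Under Section 3.2 the DSMB review may take place when the first patient has completed Day 30 and the other three have completed only Day 14. The longest stated DLT window, for necrosis, is two weeks from administration. With the second dose on Day 14 ± 1, that window closes between Day 13 + 14 = 27 and Day 15 + 14 = 29. It can still be open for three of four patients at the earliest review, and the plan itself provides a sentence for this case.

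**3. Each reading followed through**, with exactly one late DLT and no other. In the expansion column, one to four patients of the higher cohort have already been treated.

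| Late DLT in | One-DLT rule still applies | Only the late-DLT sentence applies, escalation resumed |
|---|---|---|
| Cohort I, Cohort II open | MTD 4 mg; no Cohort III; N = 6 + (1 to 4) = 7 to 10 | 16 mg reached; N = 12; no MTD rule triggered |
| Cohort II, Cohort III open | MTD 8 mg; N = 4 + 6 + (1 to 4) = 11 to 14 | No escalation step left to delay, so no action; N = 12; no MTD rule triggered |

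**4. How often?** The documents give no DLT rate, so every figure here rests on assumed values.

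- Let p be the risk, in each of the three patients still in follow-up, of a DLT that becomes evident after the review. The chance of exactly one is 3p(1−p)². At p = 0.02 this is 3 × 0.02 × 0.9604 = 5.8%; at p = 0.05, 13.5%; at p = 0.10, 24.3%.
- Alternatively, let p be the overall per-patient DLT risk and f the share of it that falls after the review. The chance of exactly one late DLT and no other among the four is 3pf(1−p)³. At p = 0.05, f = 0.25 this is 3 × 0.05 × 0.25 × 0.857 = 3.2%; at p = 0.10, f = 0.50, 10.9%; at p = 0.30, f = 0.75, 23.2%. Requiring also no DLT in the two added patients multiplies by (1−p)². Over p from 0.05 to 0.30 and f from 0.25 to 0.75, that gives about 3% to 15%.

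The two calculations together span about 3% to 24% for a given cohort that has been escalated. They are upper-end because they assume that the DSMB meets at the earliest permitted moment and the next cohort opens at once.

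**The case against.** A reader might infer that the synopsis and Section 3.2 give opposite orders, so that the same data yield two different MTDs. The documents do not support that, for two reasons. Section 3.2 contains the expand-and-name-the-MTD rule itself, in its bullets, with no time limit of its own. And the late-DLT sentence names no MTD at all. The most that can be said is that one reading defines an MTD and another leaves it undefined. The ambiguity lies inside Section 3.2 as well as between it and the synopsis.

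The sentence can also be read as a temporary hold on top of the bullet, in which case both sections give the same MTD. That reading is permissible, but the text does not establish it. It leaves the sentence without effect, because the bullet already ends escalation, and it does not explain why the bullets are tied to the decision to move up a dose.

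Nor should a reader infer that a late Cohort II DLT would go unwatched. Under Section 3.2 the DSMB monitors safety for the full 12 months, and under Section 3.5.3 the sponsor may stop the study for safety. Those are general powers; they do not say how the event enters the MTD.

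The probabilities are rightly open to challenge. Acute anaphylaxis and fever within 24 hours would mostly show before another cohort could open, so late DLTs would be mainly necrosis. Finally, the flowchart (Figure 3) is not shown in the text available and was not checked; it may favour one reading.

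**Conclusion.** The concern stands in this form: the rules for one DLT observed after escalation are not consistent, and the text does not say which applies. After a late Cohort I DLT, the difference is an MTD of 4 mg with no Cohort III against treatment up to 16 mg with no MTD rule triggered. After a late Cohort II DLT, it is an MTD of 8 mg against no action. The conclusion rests on the wording and not on the 3% to 24%, which depends wholly on assumed rates. It assumes that Figure 3 does not resolve the matter. It concerns a single DLT only, so the two-DLT stopping rules do not settle it. Because the MTD is the stated primary goal and the plan foresees the event, this should be corrected before it can arise.

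**What to change.** Reconcile the synopsis rule, the Section 3.2 one-DLT bullet and the Section 3.2 late-DLT sentence into one late-DLT rule, worded identically in the synopsis and Section 3.2. It should state:

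- whether the one-DLT expansion and MTD rule applies once escalation has occurred, including when Cohort III is already open;
- what the late DLT does to the MTD;
- the status of the open higher cohort during DSMB review, covering both enrolment and pending Day 14 injections.

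Check Figure 3 and the DSMB charter against the result. Which clinical rule to adopt is for the sponsor and the DSMB.

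The cost is protocol wording in two places and matching text in the charter, with no new procedures. The downside is less discretion after a late DLT.
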